6.2.4 Follow-up visits and other data collection

Follow-up assessments at 3 and 6 months include the following (all described above in the baseline assessment section):

- Blood draws/laboratory tests
- Weight measurement
- Computerized tests of behavioral impulsivity and cognitive tasks
- Health history/medication changes
- Online battery of self-report questionnaires; may be completed at in-person visit if preferred (described above)
- 24-hour dietary recall
- Craving EMA

We aim to complete the 3 and 6 month visits with all participants within a 2-3 week window at these timepoints.

At-Home Ketone Monitoring: Participants will be given a home ketone monitoring device (Precision Xtra® System) and ketone strips, which measure beta-hydroxybutyrate. This is a glucometer device that also measures ketones from finger-stick blood if ketone strips are inserted instead of glucose

strips. The device store data, which will be checked periodically during class sessions to confirm accuracy of self-reported measurements. *Frequency:* Participants will be asked to measure ketones before dinner 3 times a week for approximately 4 weeks during the intervention (to provide more intensively self-monitoring when starting the diet) and twice weekly thereafter to monitor ketosis/diet adherence. We will use the EMA system to send requests to check ketone levels and report values back. During study visits, participants will be asked to bring in the meter and staff will download data on devices to provide a check on accuracy of participant reported measures.

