9. STATISTICAL CONSIDERATIONS

9.1 General Design Issues

Our overall hypothesis is that improved ability to manage food cravings and emotional eating is a key mechanism through which mindfulness-enhancements can improve dietary adherence. In the initial R61 phase, we will look for preliminary evidence for several hypothesized pathways by which the MBI components will influence dietary adherence.

We have several hypothesized pathways by which the MBI components will influence dietary adherence. These pathways and their associated measures are as follows:

1. Primary: Enhanced ability to address food cravings/decreased impulsivity. We have three key measures: (1) frequency of eating in response to cravings (EMA); (2) frequency of eating high carbohydrate/sweet foods in response to cravings (EMA); (3) the Delayed Discounting task or Relative Reinforcing Value of Food task.
2. Decreased stress- and emotion-related eating. We will use two key measures: (1) Palatable Eating Motives Scale (PEMS), for stress-related eating. (2) The Emotional Overeating Questionnaire for other emotion-related eating. We will also use the EMA method above to assess eating in response to emotions.
3. Improved resilience (resumption of dietary adherence) when dietary non-adherence occurs. Our key measure will be the time from a ketone measure of < 0.2 mmol/L to higher levels of > 0.2 mmol/L, indicating a return to nutritional ketosis after a period of consuming foods that depress ketosis.

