9.5.2 Secondary Outcomes

Secondary mechanistic outcomes: We have four additional mechanistic measures to assess our hypothesis that mindfulness training will enhance dietary adherence:

- Enhanced ability to reduce craving-related eating/decreased impulsivity as measured by the Delayed Discounting or Relative Reinforcing Value of Food task.
- Decreased stress-related eating as measured by the Palatable Eating Motives Scale (PEMS) subscale for stress-related eating as a coping mechanism.
- Decreased emotion related eating as measured by the Emotional Overeating Questionnaire.
- Improved resilience (resumption of dietary adherence) after dietary non-adherence occurs. Our key measure will be the time from a ketone measure of < 0.2 mmol/L to higher levels of > 0.2 mmol/L, indicating a return to nutritional ketosis after a period of consuming foods that depress ketosis.

Secondary clinical outcomes:

- Glycemic control, using HbA1c. We view improving HbA1c as the primary clinical outcome that we seek to improve in subsequent studies.
- Fasting glucose
- Homeostatic model assessment (HOMA) index of insulin resistance (computed from insulin and fasting glucose measures)
- Weight
- Adherence to diet measured by 24-hour diet recall and by ketone measures

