9.6 Data Analyses

Overall analysis approach: Preliminary analysis will be performed to confirm that key data variables are clean and complete in prepared datasets. Baseline patient characteristics will be compared between intervention groups to assess whether important characteristics were evenly distributed during randomization. General analytic approaches will include estimation of odds ratios and risk differences plus chi-square tests for categorical variables compared across groups, rates of change with confidence intervals plus McNemar's test for categorical variables compared pre/post-intervention within groups, and t-tests and multiple regression for comparing continuous variables between groups. Secondary analyses will use random-intercept-random-slope mixed effects models for all repeated measures over time, with linear splines used to estimate initial improvements, subsequent maintenance, and possible eventual backsliding.

The principal analysis will use intent-to-treat methods in which all observations will be included for individuals based on initial group assignment, regardless of adherence to the treatment protocol. As a secondary analytic method, we will also perform as-treated analyses with those who attend at least 2/3

of weekly group sessions (8/12). We recognize the challenge of missing data in assessing clinical trial outcomes. We will take extensive steps to limit missing data. Our team has extensive experience in study retention; in our SUCCEED T2DM study, outcome assessment was completed in 97% of participants at 12 weeks. For our primary mechanism measure, eating in response to cravings using EMA, data can be obtained even for persons who move or have to travel. Finally, we will employ mixed-effects models and multiple imputation methods to address missing data if there is still a substantial amount.

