For each of these measures, our primary analysis will be comparison of changes from baseline to follow-up time points between groups (see overall analysis approach above). We will also assess changes from baseline to follow-up within each group to help assess the potential effect of each intervention arm on these measures. We will also test for preliminary evidence that each of these proposed mechanisms is associated with dietary adherence. Dietary adherence will be measured two ways: (1) proportion of blood ketone measures $\geq 0.3\text{mmol/L}$; (2) proportion of kcal from carbohydrate, using 24-hour diet recall. Each of our mechanism measures are continuous variables. We will therefore assess correlations between each of the mechanism measures and the dietary adherence measures, using linear regression. Finally, we will perform initial analysis of whether there are differences in two important clinical outcomes between intervention groups: HbA1c (to examine glycemic control) and weight. These clinical outcomes should result from our intermediate behavioral outcome of improved dietary adherence. We do not expect to have adequate sample-size in either phase of this study to address this question, but believe that preliminary assessment of these outcomes should be performed in case there are dramatic differences between groups even with limited sample size.

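### The resilience outcome is the time between ketone readings, so the drop from three to two tests a week lengthens recorded recovery with no true change

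*Combined protocol and SAP*

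**What the plan says.** Sections 1.2, 9.1 and 9.5.2 define the resilience measure in the same way. In 9.5.2 the words are "the time from a ketone measure of < 0.2 mmol/L to higher levels of > 0.2 mmol/L". It is the key measure for one of the three hypothesised pathways and is listed as a secondary mechanistic outcome.

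Section 6.2.4 sets the testing schedule: "Participants will be asked to measure ketones before dinner 3 times a week for approximately 4 weeks during the intervention", then "twice weekly thereafter to monitor ketosis/diet adherence". Tests are done at home on prompt ("We will use the EMA system to send requests to check ketone levels and report values back"), and the meters store their data, which staff download at visits.

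Section 9.6 states that "Each of our mechanism measures are continuous variables". It plans comparisons of change between groups, changes within each group, and linear regression against dietary adherence. As secondary analyses it plans mixed models for repeated measures, with "linear splines used to estimate initial improvements, subsequent maintenance, and possible eventual backsliding". It has no term for the spacing of readings, no method for interval-censored times and no rule for skipped ketone tests. Its missing-data text is general.

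**The concern.** Recovery happens at some unobserved moment between the last low reading and the first high one. The plan records it as if it happened at the high reading. The recorded time is therefore a whole number of testing gaps and never less than one. When the gap widens, the recorded time lengthens even if participants recover exactly as fast as before.

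At stake is the reading of any trend in resilience. An apparent slowing after about week 4 could come from the testing schedule alone. The schedule of evaluations in 6.1 shows no ketone monitoring at baseline, so a change from baseline is not available for this outcome. What remains is a direct comparison of arms or a course over time, and a course over time that starts with the intervention crosses the frequency change.

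A second route is testing behaviour. A skipped test is not a missing outcome under this definition. It changes which readings delimit the lapse, so multiple imputation of missing outcomes would not correct it.

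**Working it through.** The plan states no expected value, power or sample size for this outcome, so there is no figure to reproduce.

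**Inputs from 6.2.4.** Three tests a week give a mean gap of 7/3 = 2.33 days. Two a week give 7/2 = 3.5 days. The shortest recordable recovery therefore rises, on average, by a factor of 3.5/2.33 = 1.5.

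**Assumption.** The documents give no recovery times. I take exponential recovery with mean m from 1 to 10 days.

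**Step 1: effect of the frequency change.** For even gaps g, the number of gaps to the first high reading is geometric with success probability 1 − exp(−g/m). The expected recorded time is

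E = g / (1 − exp(−g/m)).

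For m = 2: at g = 7/3, 2.333/(1 − 0.311) = 3.39; at g = 3.5, 3.5/(1 − 0.174) = 4.24.

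| True mean m (days) | 3 a week | 2 a week | Difference | Ratio |
|---|---|---|---|---|
| 1 | 2.58 | 3.61 | 1.03 | 1.40 |
| 2 | 3.39 | 4.24 | 0.85 | 1.25 |
| 3 | 4.32 | 5.08 | 0.77 | 1.18 |
| 5 | 6.26 | 6.95 | 0.70 | 1.11 |
| 7 | 8.23 | 8.90 | 0.66 | 1.08 |
| 10 | 11.21 | 11.85 | 0.64 | 1.06 |

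Differences and ratios use unrounded values.

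**Step 2: check by simulation.** Tests fell on days 0, 2, 4 of each week versus days 0, 3, with spells in ketosis averaging 14 days (also an assumption). Exponential lapses with means of 1 to 7 days gave ratios of 1.40 down to 1.11, a rise of about 1.0 to 1.1 days. Fixed lapses of 1 to 7 days gave ratios between 1.04 and 1.56, a rise of about 0.2 to 1.4 days. Recorded recovery lengthened in every scenario.

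**Step 3: contrast between arms at equal testing.** The planned t-tests and regressions compare means in days, so the loss is shown in days.

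- True 3 versus 2 days (1.00 day): recorded as 4.32 − 3.39 = 0.93 at three a week, and 0.85 at two a week (5.083 − 4.236).
- True 5 versus 3 days (2.00 days): 97% retained at three a week, 93% at two.
- True 2 versus 1 day (1.00 day): 0.80 retained at three a week, 0.63 at two.

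**Step 4: skipped tests at two a week (simulation; skip rates assumed).**

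- Skipping unrelated to ketone level, true mean 3 days: 5.6 days with none skipped, 6.2 with 10%, 7.0 with 25%, 9.8 with 50%.
- Skipping only while ketones are low, exponential lapses of mean 3 days: 5.65 days with none skipped, 5.72 with 75% of the low-ketone tests skipped, so essentially no change.
- Skipping only while ketones are low, fixed 7-day lapses: 7.9 days falls to 6.8 with 50% of the low-ketone tests skipped.

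**The case against.** The strongest reply is that the resilience hypothesis is about the effect of mindfulness training, which is a contrast between arms. Both arms follow one schedule, so the frequency change acts on both. This stands. A reader might infer that the outcome cannot test the hypothesis at all, and the documents do not support that: at equal testing the direction of the contrast is kept and most of its size in days survives, except for very short lapses. Expressing the loss as a ratio (a true +50% recorded as +20%) makes it look larger than it is for analyses that compare means.

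A reader might also infer that the spline models would report backsliding. That has not been shown. Section 9.6 makes those models secondary, gives no knots, and does not say whether resilience enters lapse by lapse or as one summary per person. The change is a single early step, at about week 4 of a 26-week course.

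Nor can it be said that people who skip tests will always look less resilient. That holds only if skipping is unrelated to ketone level, and no skip rate is given. Prompts and stored meter data may also keep skipping low.

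Finally, the size rests on assumed recovery times, and the larger percentages need short lapses. This also stands. But none of these replies removes the distortion from within-group and over-time comparisons, which 9.6 also plans.

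**Conclusion.** The concern holds in limited form. Under even gaps and exponential recovery with a mean of 1 to 10 days, the fall in testing frequency alone adds about 0.6 to 1.0 day to mean recorded recovery (+40% at a true mean of 1 day, +6% at 10 days). Other lapse shapes and a weekday schedule give about 0.2 to 1.4 days. Any within-group or over-time analysis that spans the change carries this artefact.

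The schedule by itself does not bias the comparison of arms at equal times. It attenuates it by about 7% to 15% in days for a contrast of 3 versus 2 days, and by 20% to 37% for 2 versus 1 day. If the arms differ in how they test, the comparison could be biased in either direction.

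This is a secondary mechanistic outcome and the sample size does not depend on it. The case for acting is that the artefact is foreseeable and cheap to remove.

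**What to change.** In 9.5.2 and 9.6, stop treating the elapsed time between readings as an exact continuous value. Use one of two analyses:

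- an interval-censored time-to-recovery model, with recovery placed between the last low and the first high reading; or
- a discrete-time model of the chance that a low reading is followed by a high one, with days since the previous reading as a term.

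Include testing phase (three versus two a week) in any over-time or within-group analysis. Also report the number of tests completed by arm and phase, so that differences in testing behaviour are visible.

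The cost is revised wording and slightly more analysis, using reading dates from the prompts and meter downloads and no new measurements. Intervals will be wider, because the gap is no longer treated as exact. Neither model recovers lapses that fall wholly between two readings, or fully corrects for skipping that depends on ketone level, so both should be stated as limitations.

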4. SELECTION AND ENROLLMENT OF PARTICIPANTS

4.1 Inclusion Criteria

Participants must meet all of the inclusion criteria to participate in this study:

1. History of T2DM mellitus. If taking insulin, screening labs will include C-Peptide to rule out T1DM. The study intervention is not designed for people with Type 1 diabetes who make no insulin.
2. HbA1c > 6.5% and < 12.0% at screening. The lower limit confirms the diabetes diagnosis. Persons with a HbA1c > than 12% typically need immediate attention to the medical regimen, and we aim to have this done before entering the trial to better separate the effects of improved medical regimens from the diet intervention. Potential participants with a HbA1c > 12% can be enrolled once glucose control is improved.
3. Experience food-related cravings most days of the week and eat in response to these cravings regularly. A key hypothesis is that our mindfulness approach will reduce cravings and craving-related eating, and this is primary mechanistic outcome. Thus we need to recruit participants who experience this.
4. Aged 18 years old and older. We are not enrolling younger children as they may need an intervention that is better tailored to children.
5. Able to engage in light physical activity. We will be recommending physical activity as part of the intervention.
6. Willing and able to participate in the interventions. Must be interested in following a carbohydrate- restricted diet, willing to learn about mindful eating and behavioral strategies for following prescribed diets, have sufficient control over their food intake so that they can follow either diet, and otherwise be able and willing to participate in the intervention. Intervention content must be practiced to evaluate whether it is effective.
7. Have smartphone and are willing to use it on a regular basis for data collection (e.g. craving EMA assessment).
8. Ability to speak English. Groups will be conducted in English, and we do not have the capacity, given the resources available in this proposal, to translate all course material and conduct groups into another language. We enrolled Hispanic participants into the pilot study who were fluent in English, and expect to do this in the proposed study.

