5.3 Concomitant Interventions

5.3.1 Allowed Interventions

Participants are allowed to continue on medications prescribed by their physicians, except for those outlined in the exclusion criteria: oral or parenteral glucocorticoid treatment; weight loss medications or supplements such as Alli or amphetamine-based drugs that are believed to effect on weight.

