6.2.2 Enrollment, Baseline, and/or Randomization

Enrollment

Participants will become enrolled upon randomization, after meeting all screening criteria and completing all of the baseline assessment procedures.

Baseline Assessments

Those who complete the consent visit and whose screening labs are within range will complete the following baseline assessments from home/online: Qualtrics questionnaire (to assess baseline eating behavior, mood, stress, etc), 24-hour diet recall, and baseline blood draw at LabCorp convenient to them. Those whose screening Craving EMA was completed more than 4 weeks before the class start date will repeat this assessment in order to get baseline data more proximal to when the intervention starts.

Blood draws and lab tests will be done at LabCorp.

Test	Rationale	Screening	Baseline	Follow-up (3 & 6 mos)
HbA1c	Overall glucose control	x	x	x
C-peptide (for those on insulin)	Confirms T2DM in those on insulin	x		
TSH	Rule out untreated thyroid disorder	x		
Comprehensive Metabolic Panel	Rule out liver and kidney dysfunction	x		
Glucose, Plasma (fasting)*	Used to calculate HOMA-IR		x	x
Insulin*			x	x
hsCRP	Examine effects of the diet on		x	x
Lipid Panel	cardiometabolic and inflammatory		x	x
NMR LipoProfile® (Without Graph)—includes lipids	markers		x	x

24-hour dietary recall: Despite limitations of self-report measures in assessing dietary intake, they remain an important tool to assess dietary adherence. 24-hour diet recall provides a measure that complements the ketone measure by providing overall diet composition information that cannot be obtained from ketone measures. We will use the University of Minnesota's Nutrition Data System for Research (NDSR) software to perform 24-hour diet recall (<http://www.ncc.umn.edu/products/>). This is a widely-used dietary analysis program that enables the collection of multiple 24-hour diet recalls and encompasses multiple foods appropriate for diets of type 2 diabetic patients. Dietary recalls will be administered by trained dietetics volunteers by co-investigator [name], a nutrition epidemiologist with extensive history of conducting 24-hour recalls. Recalls will be entered into the NDSR software immediately after completion. Dietary recalls will be conducted without prior notification to avoid changes in diet on the reporting day.

Craving EMA: We hypothesize that a key behavior mechanism by which training in mindfulness can

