2. Hypoglycemia: The carbohydrate restricted diet may lead to decreases in glucose levels. In persons receiving medications such as sulfonylureas or insulin, this could increase the risk of hypoglycemia if appropriate medication adjustments are not made while the participant is transitioning into nutritional ketosis (once in nutritional ketosis, beta-hydroxybutyrate as a preferred CNS fuel offers some protection against symptomatic hypoglycemia.⁵⁶). In our pilot study, we used a medication reduction algorithm that resulted in no episodes of hypoglycemia. For the proposed study, we will use a similar algorithm.

Initial HbA1c	Initial medication reduction
6.5-7.0%	
 • Continue: Metformin, TZD • Reduce by 50%: Basal insulin • Stop: Secretagogue, prandial insulin, pre-mixed insulin, acarbose, GLP-1 ag/DPP4 inhibitor
7.1-8.0%	
 • Continue: Metformin, TZD • Reduce by 50%: Basal insulin, pre-mixed insulin, secretagogue, GLP-1 ag/DPP4 inhibitor • Stop: Acarbose, prandial insulin
8.1-12%	
 • Continue Metformin, TZD, secretagogue, basal insulin, GLP-1 ag/DPP4 inhibitor • Reduce by 50%: Pre-mixed insulin, • Stop: Acarbose, prandial insulin

TZD: thiazolidinedione; secretagogue: sulfonylureas and meglitinides; GLP-1 ag: glucagon like peptide 1 agonist; DPP-4 inhibitor: dipeptidyl peptidase 4

For the first 6 weeks of the trial, participants on non-insulin medications will be asked to check blood glucose (BG) fasting and pre-dinner. If taking insulin, participants will be asked to check BG before each injection (standard of care). BGs will be reviewed on a weekly basis by study physicians, including an endocrinologist. If the majority of BG values drop below 110, or there are other concerning BG patterns, we will reduce/stop medications in the following order:

1. Pre-mixed insulin
2. Secretagogue
3. GLP-1 ag/DPP4 inhibitor
4. Basal Insulin

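### HOMA insulin resistance is planned without a restriction to participants not on insulin, although insulin users are eligible and the protocol reduces insulin doses after the baseline draw

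*Combined protocol and SAP*

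**What the plan says.** Sections 1.2 and 9.5.2 name HOMA as a secondary clinical outcome: "Homeostatic model assessment (HOMA) index of insulin resistance (computed from insulin and fasting glucose measures". The laboratory table in section 6.2.2 schedules fasting glucose and insulin at baseline, 3 and 6 months, with the stated rationale "Used to calculate HOMA-IR".

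Insulin users can enter the trial. Section 4.1 states: "If taking insulin, screening labs will include C-Peptide to rule out T1DM". Section 5.3.1 adds: "Participants are allowed to continue on medications prescribed by their physicians, except for those outlined in the exclusion criteria". Insulin is not among those exclusions. Section 7.1 gives insulin users their own monitoring instruction: "If taking insulin, participants will be asked to check BG before each injection (standard of care".

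The medication table in section 7.1 then changes insulin according to initial HbA1c:

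- **6.5-7.0%:** basal insulin is halved, and a further entry reads "Stop: Secretagogue, prandial insulin, pre-mixed insulin, acarbose, GLP-1 ag/DPP4 inhibitor".
- **7.1-8.0%:** "Reduce by 50%: Basal insulin, pre-mixed insulin, secretagogue, GLP-1 ag/DPP4 inhibitor", with prandial insulin stopped.
- **8.1-12%:** basal insulin is continued, pre-mixed insulin halved and prandial insulin stopped.

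Further reductions follow home glucose readings, with pre-mixed insulin first and basal insulin fourth in the order.

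The row "C-peptide (for those on insulin" in the laboratory table is marked at screening only. Section 9.6 includes every observation by assigned group and has no rule for insulin users or dose changes. Medication changes are collected at follow-up (section 6.2.4), but no analysis of them is described.

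**The concern.** HOMA is proportional to fasting glucose times measured fasting insulin. It is read as insulin resistance on the footing that the insulin is the person's own response to that glucose. In someone who injects insulin, part of the measured value may be drug, and its amount is set by prescription. Here the prescription is changed between the baseline and follow-up draws, under the protocol's own procedure.

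This differs from the familiar problem of medication changes and HbA1c. After a drug change HbA1c still measures glycaemia, and the question is only what caused the change. In an insulin user HOMA may no longer measure the quantity it is named for.

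At stake is the reading of one secondary outcome. Section 2.2 cites improved insulin resistance as an expected benefit of the diet, so a fall in HOMA would readily be taken as confirmation. Because C-peptide is not drawn after screening, the planned samples would not allow a C-peptide-based analysis of change later.

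**Working it through.** The plan gives no sample size, SD or expected effect for HOMA, so there is no figure of its own to reproduce. The check has two parts: whether the documents handle the problem, and how large it could be.

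**Timing.** Baseline assessments are completed before randomisation, and randomisation is about 2 weeks before classes start (section 6.2.2). The initial medication reduction accompanies the move onto the diet (section 7.1). It therefore falls between the baseline and 3-month draws.

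**Handling.** Sections 4.2, 5.3, 6.2.2, 6.2.4, 9.2, 9.5.2 and 9.6 contain no visible restriction, substitution of C-peptide, dose adjustment or sensitivity analysis for HOMA. Randomisation is stratified by BMI only.

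**Size.** The documents give neither the share of insulin users nor the injected share of measured insulin. Both are assumed below.

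- *u* = share of participants on insulin: 10%, 20%, 30% (6, 12 or 18 of the 60 in R61)
- *e* = share of measured insulin that is injected and detected: 25%, 50%, 75%
- *c* = fraction by which the dose is cut: 0.5 if halved
- glucose and endogenous insulin fixed; equal baseline HOMA in users and non-users

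*One insulin user.* HOMA = glucose x insulin / 405. With an assumed 140 mg/dL and 20 uU/mL, this is 140 x 20 / 405 = 6.91. After the cut, measured insulin is 20 x (1 - e x c):

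| e | HOMA after halving | Change |
|---|---|---|
| 25% | 6.05 | -12.5% |
| 50% | 5.19 | -25% |
| 75% | 4.32 | -37.5% |

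*Arm mean.* Change = -u x e x c.

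- Low: 0.10 x 0.25 x 0.5 = 1.25%
- Middle: 0.20 x 0.50 x 0.5 = 5%
- High: 0.30 x 0.75 x 0.5 = 11.25%

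If the injected insulin were stopped rather than halved (*c* = 1), each figure doubles, to 2.5%, 10% and 22.5%.

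*Offset by glucose.* With *e* = 50% and the dose halved, insulin is multiplied by 0.75. A 10% rise in glucose would give 0.75 x 1.10 = 0.825, a fall of 17.5% rather than 25%. Full offset needs glucose to rise by 1/0.75 - 1 = 33%.

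*Between arms.* If the cuts are alike in both arms, the shift largely cancels. If a further *d* of the insulin users in one arm receive an extra halving, the difference is -d x u x e x c. With *d* = 20 percentage points, *u* = 20% and *e* = 50%, this is 0.2 x 0.2 x 0.5 x 0.5 = 1%. Over *d* = 10-30 points and the ranges above, it runs from 0.1 x 0.1 x 0.25 x 0.5 = 0.1% to 0.3 x 0.3 x 0.75 x 0.5 = 3.4%.

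*Chance imbalance in insulin users, 30 per arm.* The SD of the difference in proportions is sqrt(2u(1-u)/30), which is 0.077, 0.103 and 0.118 for *u* = 10%, 20% and 30%. Multiplied by e x c = 0.25, this gives an SD of about 1.9%, 2.6% and 3.0% in the difference between mean HOMA values.

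**The case against.** Several points on the other side have force.

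- **The missing footnote.** In the laboratory table the glucose and insulin rows carry an asterisk, and its footnote is not in the text available for review. It may say only that the sample is fasting, but a rule for insulin users cannot be excluded. This stands as a reservation. No other section hints at such a rule.
- **The example holds glucose fixed.** If less insulin keeps fasting glucose at the same level, that can itself mean lower resistance; if resistance is unchanged, glucose would be expected to rise. This also stands. The figures show how the index responds to dose and do not prove that resistance stayed constant. They still show that the index cannot separate the two in insulin users.
- **HOMA carries little weight.** For clinical outcomes, section 9.6 names only HbA1c and weight for comparison, and concedes that the sample is inadequate. The within-group analyses described there read most naturally as applying to the mechanism measures. HOMA is nevertheless a listed outcome, and the general approach in section 9.6 covers repeated measures over time.

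A reader might also infer more than the documents support:

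- *That every insulin user's dose is cut.* Someone on basal insulin alone at HbA1c 8.1-12% is affected only by a later, glucose-driven step.
- *That HOMA is invalid for the whole sample.* The problem is confined to insulin users and depends on an assay the documents do not describe.
- *That a spurious benefit is added to the arm whose glucose falls more.* The initial cuts depend on HbA1c and drug class, not on arm. Differential later cuts are plausible, since they follow glucose and staff know the assignment, but this is a possibility only.
- *That secretagogue users should be left out too.* Those drugs act on the person's own insulin, so the argument about injected insulin does not reach them.

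**Conclusion.** The point holds in a limited form. As far as the available text shows, HOMA would be computed for all participants, including insulin users whose injected dose the protocol may reduce between draws. For those participants, to the extent that the assay detects injected insulin, the index does not measure their own insulin resistance and can fall with the dose.

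The shift in an arm's mean is about -1% to -11%. That rests on 10-30% insulin users, 25-75% of measured insulin injected, a halved dose, fixed glucose and endogenous insulin, and equal baseline HOMA. None of these comes from the documents, and a rise in glucose would reduce the shift. Change over time within an arm is affected most directly. The comparison between arms is distorted only if later cuts, or the number of insulin users, differ by arm; on the same ranges, differential halving gives roughly 0.1% to 3.4%.

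This affects one secondary outcome and neither the primary outcome nor any power statement. It is worth correcting because the correction is cheap.

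**What to change.** First check the footnote to the starred glucose and insulin rows in section 6.2.2. If it does not already settle the matter, amend sections 9.5.2 and 9.6 as follows:

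- Define the main HOMA analysis set as randomised participants not taking insulin at baseline, analysed by assigned arm. Take baseline insulin use from the last medication record before randomisation.
- Keep participants who start insulin later in that set. Excluding them would condition on an event after randomisation and weaken the comparison.
- Report HOMA in all participants only as a sensitivity analysis.
- Report insulin starts and dose changes by arm, using the medication data already collected at follow-up.

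Medications are recorded at the consent visit and updated at 3 and 6 months, so no new visit or sample is needed. The cost is sample size on one secondary outcome: at 10-30% insulin users, 42-54 of 60 would remain in R61 and 84-108 of 120 in R33. The HOMA result would then describe only participants not on insulin at baseline. No change to the medication algorithm is proposed.
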